5.1.1 Screening and Informed Consent

The study will be described in detail to participants and their parents/legal guardians at an initial visit. If the participant and family agree to participate in the study, the applicable assent, consent and HIPAA documents will be signed (see Appendix 4). After informed consent has been obtained, a screening assessment will be performed. The screening assessment will include a medical history, physical examination and laboratory tests. The site psychologist will also administer the primary outcome measures (see section 5.1.4.1) and an abbreviated IQ measure which is estimated to take 50 minutes to complete. To be eligible to participate in the treatment phase, patients must have an impairment on at least one of the primary outcome measures of visual spatial learning or sustained attention (≥ 1 SD below the normative mean) and an IQ equal to or above 70. Unless the patient has undergone an IQ test within six months of screening, IQ will be assessed using the Wechsler Abbreviated Scale of Intelligence (WASI; Wechsler, 1999). If the participant has recently completed an IQ test (within six months of screening), then this score will be used for the purposes of screening. Examples of acceptable IQ tests include (but are not limited to) the WASI, the Wechsler Intelligence Scale for Children 4th Edition (WISC-IV), and the Stanford-Binet Intelligence Scales 5th Edition (SB-V).

If the child fails to satisfy the screening criteria, parents will be verbally informed of the reason why the child did not meet the criteria. If the reason for exclusion was a Full-Scale IQ less than 70, parents will be verbally informed of the range of the child's IQ score and that it may indicate the presence of an intellectual disability. Parents will be advised that only a brief assessment of IQ was conducted and that the child's performance may vary due to motivation, attention and fatigue. It will be recommended to parents that their child undergo a full IQ assessment to obtain further information about their child's intellectual functioning. Upon request, results of the IQ test will be provided to parents in a written report.

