5.1.2 History and Physical Examination

A complete medical history and physical examination (including neurological examination) will be performed initially to confirm each participant's NF1 diagnosis and to document any complications that they might have from the disease. Height, weight, head circumference, blood pressure, and pulse will be recorded. Patients will also be given a list of medications to avoid while on this study. To be eligible participants must have not taken any stimulant medications for at least 30 days or more and agree to remain off stimulant medication for the duration of the study.

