6.4 Drug Dosage and Possible Interactions

The selection of the maximum dose of Lovastatin to be used in this study, 40 mg/day, is based on the tolerability of the drug when used for heFH and the results of the Phase I study examining safety and tolerability of Lovastatin in children with NF1 (Acosta et al., submitted). Participants will commence at 20 mg/day for two weeks and escalate to the 40 mg/day dose in week 3.

Approximately 40% of children with NF1 are diagnosed with comorbid ADHD, many of whom are treated with psychostimulant medication such as methylphenidate and/or dextroamphetamines. In order to minimize recruitment bias and ensure recruitment targets are met, patients taking methylphenidate and/or dextroamphetamines will be eligible for this study.

The predominant metabolic pathway of methylphenidate is de-esterification to form pharmacologically inactive d- or l-ritalinic acid (Patrick et al 1987). Metabolism of methylphenidate when used by oral administration undergoes a stereoselective clearance to ritalinic acid (CES1A1 is the major enzyme responsible) before entering systemic circulation (Sun et al, 2004). Methylphenidate does not use the microsomal cythochrome P450 in the liver for its metabolism (Sun et al 2004; Patrick et al 1987). Dextroamphetamines are metabolized by the cythochrome P450 in liver. However the isoenzyme responsible for its metabolism is the CYP2D6 (Adderall Medication Guide, Shire, Nov. 2010). Instead, lovastatin is metabolized by the CYP3A4 (Ritalin® Medication Guide, Novartis, 2010). There are not described interactions or competitive mechanism between dextroamphetamines and lovastatin.

Although limited by a small sample size, results of the Phase I study provide some evidence for the inclusion of patients on stimulant medication (Acosta et al., submitted). A total of 23 patients with NF1 (10-17 years of age) completed 12 weeks of treatment with Lovastatin. Nine patients had a diagnosis of ADHD and five of these patients were taking a stable dose of stimulant medication during the course of the study. Calculation of Reliable Change Index for individuals indicated significant improvements on both verbal and nonverbal memory measures in approximately 40% of participants regardless of whether they were off or on methylphenidate.

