6.7 Adverse Event Monitoring (UK sites please refer to Appendix 10)

Participants will be monitored closely for medication side effects with a diary and with laboratory testing as indicated in the Study Procedures section (see of the protocol (see Section 5). Adverse events will be addressed immediately as described in Section 6.8. Participants will also be closely followed clinically at least once per month while on the study medication by the site physician. The Side Effects Checklist and Adverse Event Monitoring Form will be used to assess participants at every visit or phone contact.

Participants will be monitored for adverse events regularly throughout the study. Adverse events are any unfavorable or unintended sign (including abnormal laboratory findings), symptom or disease temporarily associated with the use of medical treatment or procedure regardless of whether it is considered related to the medical treatment or procedure (attribution of unrelated,

unlikely, possible, probable, or definite). Life-threatening adverse events are any adverse event that places the participant at an immediate risk of death from the reaction. Serious adverse events are any event occurring at any dose level that results in any of the following outcomes: death, a life-threatening adverse event, inpatient hospitalization, prolongation of an existing hospitalization, a persistent/significant disability/incapacity, and other medically significant events. Unexpected adverse events not listed above may also occur.

All observed or volunteered adverse events will be recorded on the Adverse Event form. Events involving adverse drug reactions, illnesses with onset during the study or exacerbation of pre-existing illnesses will be recorded. Objective test findings, such as abnormal lab values, that result in drug dosage changes will also be recorded.

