6.8 Adverse Event Reporting

Adverse events will be graded according to the Cancer Therapy Evaluation Program's; Common Terminology Criteria for Adverse Events Version 4 (CTCAE), which can be downloaded from <http://ctep.cancer.gov>. A severity grading of side effects related to Lovastatin use can be found in Appendix 7. The principal investigator at each site will determine whether the adverse event is related or unrelated to the medical treatment. If deemed to be related, the principal investigator will determine whether the adverse event is expected or unexpected. Details of the event (expected or unexpected), and whether the side effect and severity (i.e. toxicity) were included in informed consent (yes/no), will be recorded on the adverse event module form.

A justification will be recorded on the adverse event module if the observed toxicity was not included in the informed consent. For all adverse events, the investigator must pursue and obtain information to determine the outcome of adverse events and to assess whether it meets the criteria for classification of a serious adverse event. All serious adverse events require immediate notification to the Operations Center. All adverse events, whether serious or otherwise, will be followed until resolution (the patient's health has returned to his/her baseline status) or until the event has stabilized (investigator does not expect any further improvement or worsening of the adverse event). Participants withdrawn from the study due to adverse events will be followed by the investigator until resolution. All grade 3, 4 and 5 adverse events will be reviewed by the Clinical Review Committee.

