APPENDIX 3: Study Evaluation Before, During, Post Treatment and Follow-Up

Observation	Pre-treatment	2 weeks*	4 weeks (2 titrated & 2 weeks full dose)	8 weeks	12 weeks	Post-treatment 16 weeks	Follow-up (8 weeks off medication)
Phone Calls		X					
Hx and Physical	X		X	X	X	X	X
CBC	X		X	X	X	X	X
Chemistries	X		X	X	X	X	X
Neuropsychological measures	X					X	X
Pregnancy testing	X			X		X	
Side-Effects/Toxicity (Check List)		X	X	X	X	X	X
Drug compliance		X	X	X	X	X	

NB. Chemistries: Blood urea nitrogen (BUN), creatinine, glucose, alanine amino transferase (ALT), aspartate amino transferase (AST), total and direct bilirubin, CPK, Lipid profile (HDL, Cholesterol, LDL, Triglycerides). Indirect bilirubin will be computed from total and direct bilirubin serum measurements.

*Use CRFs as a guide with questions for phone follow-up

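### The side-effects checklist is first scheduled at week 2, on drug, so subjective symptoms have only an unstructured pre-dose history as comparator

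*Protocol*

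**What the plan says.** The schedule in Protocol Appendix 3 has a row "Side-Effects/Toxicity (Check List" with marks at weeks 2, 4, 8, 12 and 16 and at follow-up. The pre-treatment cell is blank. The only phone call is also at week 2. By then the child has taken 20 mg or placebo for two weeks (Section 5.2.1) and is about to "escalate to the 40 mg/day dose in week 3" (Section 6.4).

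Section 6.7 states: "The Side Effects Checklist and Adverse Event Monitoring Form will be used to assess participants at every visit or phone contact". The sentence before it describes clinical follow-up "at least once per month while on the study medication". Appendix 10 repeats both for UK sites.

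Before dosing, Section 5.1.1 says: "The screening assessment will include a medical history, physical examination and laboratory tests". Section 5.1.2 adds: "A complete medical history and physical examination (including neurological examination) will be performed initially". It gives the purpose as confirming the NF1 diagnosis and documenting complications of the disease.

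For recording, Section 6.7 says that "illnesses with onset during the study or exacerbation of pre-existing illnesses will be recorded". Section 6.8 treats an event as resolved when the patient's "health has returned to his/her baseline status". Appendix 10 defines a UK adverse event as something that appears or worsens after the study starts, and counts a pre-existing condition only if it worsens.

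**The concern.** Several safety rules refer to a child's state before treatment, but no section states that symptoms are asked about item by item before the first dose. The first answers to the checklist questions come after two weeks on study medication. If a parent then reports headaches or tiredness, the site investigator must decide whether this is new, worse or unchanged, and whether it is related to treatment, with no earlier answer to the same questions.

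Toxicity and tolerability are a stated secondary aim (Section 2.2.2). Children aged 8 and 9 are enrolled although Sections 4.1 and 6.11 acknowledge a lack of preliminary safety data at that age, so the description of symptoms within the lovastatin arm has its own value. Attribution also has consequences. Under Section 6.6, related grade 2 toxicity means withholding drug until it falls to grade 1 or lower. Under Section 5.2.3, toxicity that persists at grade 2 or above for more than 10 days off drug is a reason to leave the study. Once dosing has begun, a missing pre-dose record cannot be recovered.

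**Working it through.** The plan states no figure on this point, so the check is mainly a comparison of sections.

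**Step 1. Safety rows in Appendix 3.**

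| Row | Pre-treatment | First mark |
|---|---|---|
| History and physical | X | pre-treatment |
| CBC | X | pre-treatment |
| Chemistries | X | pre-treatment |
| Pregnancy test | X | pre-treatment |
| Side-effects checklist | blank | week 2 (phone) |

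Four of the five rows have a pre-dose value. The checklist has six marks, none before dosing.

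**Step 2. Does the text fill the blank cell?** Taken alone, the Section 6.7 sentence could cover the pre-treatment visit. Its context is monitoring on study medication, and Section 5.2.2 places the toxicity review in the treatment phase. Sections 5.1.1 and 5.1.2 list no checklist. On one reading the text agrees with the table and there is no pre-dose checklist. On the other it contradicts the table, and sites may differ in practice. Both readings call for a correction.

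**Step 3. Where baseline is used as the reference.**
- Section 6.7: exacerbation of existing illness.
- Section 6.8, and the same rule in Appendix 10: resolution.
- Appendix 10: a pre-existing condition counts only if it worsens.
- Appendix 7: grade 1 fatigue is an increase over baseline, and diarrhea is graded by the increase in daily stools over pretreatment.

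**Step 4. Which Appendix 7 items are affected.** Of 19 items, 6 are laboratory values (hemoglobin, platelets, AST, ALT, bilirubin, CPK) with a scheduled pre-treatment sample. That leaves 19 − 6 = 13 clinical items. Two of these (fatigue, diarrhea) are graded as change from baseline, and insomnia is graded only when related to treatment. These three have no meaningful pre-dose grade, so what is needed for them is the usual level. Items such as headache, abdominal pain and myalgia are graded by pain and its interference with function, and can be graded before dosing.

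**Step 5. Scale of safety estimates in a trial of this size.** This does not measure the effect of the blank cell. Inputs: 142 enrolled (Section 7.0), so 142/2 = 71 per arm if arms are equal, and an assumed recorded event rate r, the same in both arms. The 95% half-width of the difference is 1.96 × √(2r(1 − r)/71).

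| Assumed r | Half-width (percentage points) |
|---|---|
| 5% | 7.2 |
| 10% | 9.9 |
| 20% | 13.2 |
| 30% | 15.1 |

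For example, at r = 0.05: 1.96 × √(0.095/71) = 0.072. The documents give no rate of pre-existing symptoms, and nothing in them says how far, if at all, the missing checklist would move r.

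**The case against.** The strongest reply is that the plan already separates old symptoms from new ones. The UK definition covers only what appears or worsens, and Appendix 10 then tabulates adverse events so defined. Other sites have the onset-or-exacerbation rule in Section 6.7. Nothing says that raw checklist answers are tabulated. This stands. A reader might infer that no site has a new-or-worse rule, or that unchanged old symptoms will inflate event rates. The documents do not support either: inflation would require sites to depart from these recording rules. What remains is that the rules need a comparator, and the stated one is a history with no described symptom content.

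Second, a complete history and a physical with neurological examination precede dosing, and the checklist and history forms are not in the documents, so the history may capture symptoms. Participants must also be medically stable, and the PedsQL, which has a physical scale, is given at baseline. This narrows the gap. As described, however, the PedsQL yields scale scores, not a record of each symptom.

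Third, the other study-conduct row left blank before treatment, drug compliance, also concerns exposure to drug, so the pattern looks deliberate. That may explain the blank cell, but it does not provide the baseline that Sections 6.7 and 6.8 and Appendix 7 refer to.

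Fourth, randomisation and a masked placebo arm protect the comparison. This stands in full.

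**Conclusion.** The point holds as a gap in structured pre-dose symptom data, together with an ambiguity or conflict between Section 6.7 and Appendix 3. It does not mean that all baseline clinical information is missing.

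The consequence is less reliable attribution and a noisier description of symptoms within each arm. The size is unknown and may be small. It would be zero if sites apply the recording rules perfectly from the history.

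Two stronger conclusions should not be drawn. The comparison between arms is not biased, because both arms follow the same schedule under masking. The half-widths in the working do not measure the harm: they follow from assumed rates and would be the same in any trial with 71 per arm. Section 7.0 plans no test of adverse event rates, and no efficacy or sample-size figure is affected.

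The conclusion assumes that the checklist items resemble the side effects in Section 6.5.1 and Appendix 7, and that the history form has no equivalent symptom list. If it has one, the point reduces to aligning the text with the table. This is a cheap improvement, not a defect that threatens the trial.

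**What to change.** - In Appendix 3, add a pre-treatment mark for the checklist, to be completed before the first dose.
- Record presence and severity of each symptom. Use Appendix 7 grades only where they are defined without reference to baseline or treatment. For fatigue, sleep and stools per day, record the usual level.
- Reword the Section 6.7 sentence, and its copy in Appendix 10, to match the schedule.
- At all sites, use this record to judge events as new or worse than pre-dose, and tabulate them by arm on that basis.
- Leave the dose rules in Section 6.6 unchanged.

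The cost is one existing form at a visit already held, a few minutes per child, and one derived variable in the safety tables.

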APPENDIX 4: Consent/Assent

[Blank intentionally – add your site specific approved consent/assents]

APPENDIX 5: Outcome Measures: Neuropsychological Assessment

Domain	Measure	Age range	Time (mins)
Memory	*Paired Associate Learning (CANTAB)	7 yrs - adult	10
Attention	Test of Everyday Attention for Children *Score! Sky Search Creature Counting Sky Search DT	6 yrs – 15 yrs 11 mths	25
	Continuous Performance Test –II	6 yrs - adult	15
	Conners’ ADHD/DSM-IV scale (parent)	3 yrs – 17 years	10
Executive Function	Stop Signal Task (CANTAB)	7 yrs – adult	10
	Spatial Working Memory (CANTAB)	7 yrs – adult	15
	Stockings of Cambridge (CANTAB)	7 yrs – adult	10
	Controlled Oral Word Association Test	7 yrs – adult	5
	Behavior Rating Inventory of Executive Function (parent)	5 – 18 yrs	15
Visual-spatial	Judgment of Line Orientation	7 yrs - adult	10
Visual-perceptual	Object Assembly (WISC-III)	6 yrs – 16yrs 11mths	13
Motor	Motor Screening (CANTAB)	7 yrs – adult	5
Intelligence	Wechsler Abbreviated Scale of Intelligence	6 yrs – adult	30
Behavior	Behavior Assessment Scale for Children – II (parent & child)	2 – 25 yrs	20
Quality of Life	Pediatric Quality of Life Inventory (parent & child)	2 – 18 yrs	10

*Primary outcome measures.

All tests of the comprehensive test battery are administered at baseline, post-treatment and follow-up except for the Wechsler Abbreviated Scale of Intelligence, which will only be administered at screening.

APPENDIX 6: Drugs & Other Components That Interact With Lovastatin

AVOID WHILE TAKING LOVASTATIN

CYP3A4/5 – Inducers	
Carbamazepine (Tegretol)	Phenytoin (Dilantin)
Dexamethasone	Primidone (Mysoline)
Ethosuximide (Zarontin)	Progesterone (all progestins)
Glucocorticoids	Rifabutin
Griseofulvin	Rifampin
Nafcillin	Rofecoxib
Nelfinavir (Viracept)	St John’s wort
Nevirapine (Viramune)	Sulfadimidine
Oxcarbazepine (Trileptal)	Sulfipyrazone
Phenobarbital	Troglitazone
Phenylbutazone	Rifapentine
	Modafinil
CYP3A4/5 – Inhibitors	
Amiodarone	Metronidazole
Anastrozole	Mibefradil
Azithromycin (Zithromax)	Miconazole
Cannabinoids	Nefazodone
Cimetidine (Tagamet)	Norfloxacin
Clarithromycin	Norfluoxetine
Clotrimazole	Omeprazole (Prilosec)
Cyclosporine	Oxiconazole
Danazol	Paroxetine
Delavirdine (Rescriptor)	Propoxyphene
Diethylthiocarbamate	Roxithromycin
Diltiazem	Quinidine
Dirithromycin	Quinine
Disulfiram	Quinupristin and dalfopristin
Entacapone	Ranitidine
Erythromycin	Ritonavir (Norvir)
Ethinyl estradiol	Saquinavir (Invirase)
Fluconazole (Diflucan)	Sertindole
Fluoxetine	Sertraline
Fluvoxamine	Troleandomycin
Gestodene	Valproic acid (Depakote)
Grapefruit juice	Verapamil
Indinavir (Crixivan)	Voriconazole
Isoniazid	Zafirlukast (Accolate)
Itraconazole	Zileuton
Ketoconazole	

ADAPTED from Cytochrome P-450 Enzymes and Drug Metabolism: Lacy CF, Armstrong LL, Goldman MP, eds. Drug Information Handbook 8th ed. Hudson, OH; LexiComp Inc. 2000: 1364-1371.

APPENDIX 7: Common Terminology, Criteria for Adverse Events (CTCAE)

Items selected according to most common or serious side effects associated with Lovastatin

Adverse Event	0	1	2	3	4
DERMATOLOGIC					
Allergic reaction/ hypersensitivity (including drug fever)	none	transient rash, drug fever <38°C (<100.4°F)	urticaria, drug fever >38°C (>100.4°F), and/or asymptomatic bronchospasm	symptomatic bronchospasm, requiring parenteral medication(s), with or without urticaria; allergy-related edema/angioedema	Anaphylaxis
Rash/desquamation	none	macular or papular eruption or erythema without associated symptoms	macular or papular eruption or erythema with pruritus or other associated symptoms covering <50% of body surface or localized desquamation or other lesions covering <50% of body surface area	symptomatic generalized erythroderma or macular, papular or vesicular eruption or desquamation covering >50% of body surface area	generalized exfoliative dermatitis or ulcerative dermatitis
HEMATOLOGIC					
Hemoglobin (Hgb)	WNL	<LLN - 10.0 g/dL <LLN - 100 g/L <LLN - 6.2 mmol/L	8.0 - <10.0 g/dL 80 - <100 g/L 4.9 - <6.2 mmol/L	6.5 - <8.0 g/dL 65 - <80 g/L 4.0 - <4.9 mmol/L	<6.5 g/dL <65 g/L <4.0 mmol/L
Platelets	WNL	<LLN - 75.0 x 10 ⁹ /L <LLN - 75,000/mm ³	>50.0 - <75.0 x 10 ⁹ /L >50,000 - <75,000/mm ³	>10.0 - <50.0 x 10 ⁹ /L >10,000 - <50,000/mm ³	<10.0 x 10 ⁹ /L <10,000/mm ³
CONSTITUTIONAL					
Fatigue (lethargy, malaise, asthenia)	none	increased fatigue over	moderate (e.g., decrease	severe (e.g., decrease in	bedridden or disabling

		baseline, but not altering normal activities	in performance status by 1 ECOG level or 20% Karnofsky or Lansky) or causing difficulty performing some activities	performance status by >2 ECOG levels or 40% Karnofsky or Lansky) or loss of ability to perform some activities	
Dizziness/lightheadedness	none	not interfering with function	interfering with function, but not interfering with activities of daily living	interfering with activities of daily living	bedridden or disabling
Insomnia Note: This adverse event is graded when insomnia is related to treatment. If pain or other symptoms interfere with sleep do NOT grade as insomnia.	normal	occasional difficulty sleeping not interfering with function	difficulty sleeping interfering with function, but not interfering with activities of daily living	frequent difficulty sleeping, interfering with activities of daily living	-
Headache	none	mild pain not interfering with function	moderate pain: pain or analgesics interfering with function, but not interfering with activities of daily living	severe pain: pain or analgesics severely interfering with activities of daily living	disabling
GASTRO-INTESTINAL					
Abdominal pain or cramping	none	mild pain not interfering with function	moderate pain: pain or analgesics interfering with function, but not interfering with activities of	severe pain: pain or analgesics severely interfering with activities of daily living	disabling

			daily living		
Constipation	none	requiring stool softener or dietary modification	requiring laxatives	requiring manual evacuation or enema	obstruction or toxic megacolon
Diarrhea participants without colostomy:	none	increase of <4 stools/day over pretreatment	increase of 4-6 stools/day, or nocturnal stools	increase of >7 stools/day or incontinence; or need for parenteral support for dehydration	physiologic consequences requiring intensive care; or hemodynamic collapse
Flatulence	none	mild	moderate	-	-
HEPATIC					
AST	WNL	>ULN - 2.5 x ULN	>2.5 - 5.0 x ULN	>5.0 - 20.0 x ULN	>20.0 x ULN
ALT	WNL	>ULN - 2.5 x ULN	>2.5 - 5.0 x ULN	>5.0 - 20.0 x ULN	>20.0 x ULN
Bilirubin	WNL	>ULN - 1.5 x ULN	>1.5 - 3.0 x ULN	>3.0 - 10.0 x ULN	>10.0 x ULN
MUSCLE					
CPK (creatine phosphokinase)	WNL	>ULN - 2.5 x ULN	>2.5 - 5 x ULN	>5 - 10 x ULN	>10 x ULN
Muscle weakness (not due to neuropathy)	normal	asymptomatic with weakness on physical exam	symptomatic and interfering with function, but not interfering with activities of daily living	symptomatic and interfering with activities of daily living	bedridden or disabling
Myositis (inflammation/damage of muscle) Also consider CPK. Note: Myositis implies muscle damage (i.e., elevated CPK).	none	mild pain, not interfering with function	pain interfering with function, but not interfering with activities of daily living	pain interfering with function and interfering with activities of daily living	bedridden or disabling
Myalgia (muscle pain)	none	mild pain not interfering with function	moderate pain: pain or analgesics interfering with function, but not interfering with activities of daily living	severe pain: pain or analgesics severely interfering with activities of daily living	Disabling

B. TIMETABLE

As outlined in the statement of work, the general timetable of this project is as follows:

0 – 12 weeks: Initiation of the study and subject recruitment

12 – 24 weeks: Continue subject recruitment and initiation of treatment and evaluation

24 - 36 weeks: Continue recruitment initiation and implementation of the clinical trial

36 to 72 weeks: Continue study/follow-up participants

72 to 96 weeks: Final data analysis and completion of the study

Months	0 - 3	3 - 6	6-9	9-18	18-24	24-36
Study Design/Ethics/Logistics	X					
Subject Recruitment/Initiation /Evaluation		X	X	X	X	
Implementation of Trial			X	X	X	
Follow-up Participants				X	X	
Begin and Complete Final Data Analysis						X

